#### **4.5.2 Data Scopes - amended**

This section describes the coverage of the event data scopes used for the statistical analyses. Analysis sets are described in section 5.

##### **Data scope according to intention-to-treat principle (ITT)**

The ITT data scope includes all outcome events observed from randomization until the efficacy cut-off date. This will be the primary data scope for the analyses.

Analyses according to the intention-to-treat (ITT) principle will be based on the intention-to-treat analysis set (see section 5.1.1) and will include all outcome events that occur from the date of randomization and up until the efficacy cut-off date (inclusive). Subjects will be kept in the study group to which they were randomized and the follow-up period for each subject will be as long and complete as possible. This ITT data scope will be applied to the primary analysis of the primary and secondary efficacy variables and safety variables.

##### **Data scope according to treatment (on-treatment)**

The on-treatment data scope will include all outcome events observed from randomization until 2 days following permanent discontinuation of the study drug.

Analyses according to the on-treatment data scope will be based on the safety analysis set (see section 5.1.2).

This on-treatment data scope will be applied to the supportive analysis of the primary and secondary efficacy variables and safety variables.

#### **4.5.3 Censoring rules for time-to-event variables - amended**

For any time-to-event variable in this study, the following censoring rules will be applied:

##### **Censoring rules for analyses according to the intention-to-treat principle**

For analyses according to the intention-to-treat principle, randomized subjects without documentation of an event will be censored at the efficacy cut-off date or the date of the last trial contact, whatever comes first.

This censoring rule will be applied to all analyses according to the intention-to-treat principle. In the rare event that for a subject only survival status information can be retrieved at the end

of the study but no information on other outcomes, the last follow-up / trial contact where survival status information was obtained will still be used to determine the censoring date for the subject and if there were no known events up to then the subject will be considered as event-free.

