### 4.2 Handling of Non-compliance to Study Treatment or Follow up

An excessive rate of patient discontinuations from either treatment or study follow up may render the trial non-interpretable. In this study, outcome events and vital status data will be collected until the end of the study, even if patients are no longer taking study medication. This means that clinical data from all randomized patients will be collected at trial close-out as far as possible.

A subject who signed an informed consent form, and, for any reason (e.g., failure to satisfy the in- and exclusion criteria) terminates the study without being randomized is regarded as a “screening failure”.

A randomized subject who permanently discontinues study treatment before their End of treatment Visit for any reason is defined as having had a permanent discontinuation of study medication (including subjects who were randomized but never started taking any study medication). The reason for permanent discontinuation of study medication will be collected.

For subjects who permanently discontinue study medication, different options of follow-up will be discussed to collect outcome events and vital status. This can include regular study visits, regular phone calls with the patient or otherwise with the general practitioner or family relative, or a contact at the end of the study. Patients who do not agree to attend regular study visits the investigator will encourage to come to at least one final visit to perform assessments to the greatest extent possible as outlined for the End of treatment Visit.

However, all randomized subjects will be encouraged to remain on study treatment and under observation for the full duration of the study. Discontinuation of study treatment is not the equivalent to withdrawal of informed consent. In cases where subjects indicate they do not want to “continue”, investigators must determine whether this refers to discontinuation of study treatment, unwillingness to attend follow-up visits, unwillingness to have telephone contact, unwillingness to have any contact with study personnel, or unwillingness to allow contact with a third party (e.g., family member, doctor). Every effort will be made to continue to follow the subject and survival status information must be determined for all subjects at the end of the study. The expectation is that only very few subjects will have incomplete follow-up (in any form) within this trial.

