## 4.5 Data Rules

### 4.5.1 Analysis Dates - amended

For the study the following date and time window are of relevance for the analysis:

- Efficacy cut-off date:  
The efficacy cut-off date is the 5th of October 2017, the date the early stopping of the trial was officially announced.
- Trial close-out window:  
The Trial close-out window is the time period when all subjects are to return to the clinic for an End of treatment Visit.

For each subject, the following individual dates are of relevance for analysis:

- Randomization date:  
The date of randomization to antithrombotic study treatment of the subject.
- End of treatment (EOT) Visit date:  
This is the date of the EOT Visit for the individual subject.  
After the announcement of the end of the study, all subjects are to return to the clinic for their EOT Visit within the pre-specified window (Trial close-out window).  
If subjects do not have an EOT visit, the date will be missing.
- Date of the last contact prior or equal to efficacy cut-off:  
This date is defined as the date of the last trial contact or the efficacy cut-off date, whatever comes first.
- Date of the last trial contact:  
The date of the last documented contact with the subject or a third party (including data on subject survival status).  
For subjects who die after randomization the date of the last contact is set to the death date.
- Date of first double-blind dose of antithrombotic study treatment:  
The date of the first dose of rivaroxaban / aspirin study medication.
- Date of last double-blind dose of antithrombotic study treatment:  
The date of the last dose of rivaroxaban / aspirin study medication.  
For a subject with permanent discontinuation of any study medication, the corresponding last dose date(s) will be obtained from the CRF "Study Medication Discontinuation/Restart Report". If study medication was continued until the EOT visit, the date of the last dose of the corresponding study medication will be as reported on the EOT visit CRF.  
If missing or incomplete, the date of last double-blind dose of antithrombotic study

treatment is set to the latest logically possible date of antithrombotic study medication administration on or before the earliest of the subject's following dates, the date of last trial contact, the date of death, or the efficacy cut-off date, and no earlier than the randomization date.

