## **6. Statistical Methodology**

### **6.1 Population characteristics**

#### **6.1.1 Disposition**

The following will be tabulated overall and/or by treatment group:

- Study sample sizes (subjects enrolled, randomized, and valid for Safety analysis set) by region and country

- Study sample sizes by country and site
- Subject disposition
- Number of subjects and primary reasons for screening failures (only overall)
- Number of subjects and primary reasons for permanent discontinuation of study medication (by treatment group and overall for SAF)
- Number of subjects and primary reasons for discontinuation of study follow-up (by treatment group and overall for ITT and SAF)
- Number of subjects withdrew consent as well as Lost to Follow-up

Kaplan-Meier plots will be used to show:

- Time from randomization to last study medication,
- Time from randomization to last contact prior or equal to efficacy cut-off,
- Time from randomization to last trial contact

by treatment group and overall for ITT and SAF.

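### The ITT censoring rule in SAP 4.5.3 counts patients known only to be alive as free of stroke, embolism, MI and bleeding; it is wrong for non-fatal outcomes, with a small effect

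*SAP*

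**What the plan says.** SAP 4.5.3 sets one ITT censoring rule for all time-to-event variables: the efficacy cut-off (5 October 2017) or the last trial contact, whichever is earlier. For a patient with survival status and no other outcome information, "the last follow-up / trial contact where survival status information was obtained will still be used to determine the censoring date for the subject". A patient of this kind with no recorded event by that date is taken to be event-free. The SAP calls this situation rare.

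The supporting definitions point the same way:

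- SAP 4.5.1 defines the last trial contact as "The date of the last documented contact with the subject or a third party (including data on subject survival status". The last contact up to the cut-off is built on it: "This date is defined as the date of the last trial contact or the efficacy cut-off date, whatever comes first".
- SAP 4.2 requires that "survival status information must be determined for all subjects at the end of the study" and does not class a patient documented as alive at study end as lost. It adds: "The expectation is that only very few subjects will have incomplete follow-up (in any form) within this trial".
- SAP 6.1.1 plots "Time from randomization to last contact prior or equal to efficacy cut-off" and tabulates "Number of subjects withdrew consent as well as Lost to Follow-up", together with the reasons for stopping follow-up by arm.
- The ITT data scope is primary for efficacy (SAP 6.2.4, 6.2.5) and for bleeding (SAP 6.4.5).
- Protocol 5.2 allows vital status to be taken from public sources after withdrawal of consent, and from registries when contact fails.

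**The concern.** A patient should be censored at the last time at which the outcome could have been recorded. Knowing that a patient is alive settles the matter for all-cause mortality and for CV death alone. It says nothing about non-fatal stroke, systemic embolism, MI or bleeding, and a registry or public-information check cannot supply them. The rule therefore adds time in which no such event could be seen and treats it as event-free.

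Three things could be affected:

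- **Absolute rates** of efficacy and bleeding outcomes are understated. These rates feed the excess-event counts in SAP 6.6.
- **The hazard ratio** moves in favour of whichever arm has more survival-only follow-up, if the arms differ.
- **The visibility of the gap.** The time-to-last-contact plot uses the same contact date, so survival-only patients appear there as followed, and those found alive are not counted as lost. Consent withdrawals and reasons for stopping follow-up are still shown, so the gap is only partly hidden.

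No planned ITT analysis checks the rule. The analysis added to SAP 6.2.7, which counts events up to the last trial contact, relies on the same contact date. The on-treatment analysis (last dose plus 2 days) largely avoids the problem but answers a different question.

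**Working it through.** **Inputs from the plan** (Protocol 8.6, SAP 4.6): 3500 patients per arm; 2-year accrual in a 3-year study; aspirin event rate 3.8% per year; expected observed risk reduction 26% (HR 0.74); deaths 3% per year; loss to follow-up 1% per year.

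**Reproducing the plan.** The event rate is 0.9 × 4.0 + 0.1 × 2.0 = 3.8. With 450 events and HR 0.74, √(450 × 0.25) × |ln 0.74| − 1.96 = 1.234, which is 89.1% power against the stated 90%. The model below, at 1% loss, gives 428 events against about 450. It is close enough for this purpose.

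**Assumption.** The documents give no rate *l* of survival-only follow-up. The planned 1% loss is only a stand-in, because patients found alive are not classed as lost. I use 0.25% to 2% per year.

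**Model.** Event hazard *h*, death hazard *d* = 0.03, *k* = *h* + *l* + *d*, and administrative follow-up *T* uniform on 1 to 3 years. Averaged over *T*:

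- observed time *o* = (1 − e^(−kT))/k
- unobserved time *u*, from loss to death or cut-off, = (l/d) × [(1 − e^(−kT))/k − e^(−dT)(1 − e^(−(h+l)T))/(h+l)]
- rate under the rule = true rate × *o*/(*o* + *u*)

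**Equal arms, aspirin arm (h = 0.038):**

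| l per year | o (y) | u (y) | Patients, 3500·l·o | Person-years, 3500·u | Share u/(o+u) | Rate per 100 | Deaths in gap, 0.03·3500·u |
|---|---|---|---|---|---|---|---|
| 0.25% | 1.855 | 0.0050 | 16 | 17.6 | 0.27% | 3.79 | 0.5 |
| 0.5% | 1.850 | 0.0100 | 32 | 35.1 | 0.54% | 3.78 | 1.1 |
| 1% | 1.841 | 0.0200 | 64 | 69.8 | 1.07% | 3.76 | 2.1 |
| 2% | 1.822 | 0.0396 | 127 | 138.7 | 2.13% | 3.72 | 4.2 |

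The true rate is 3.80. The rate ratio, taken here as the hazard ratio, does not move in any row.

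**Unequal arms.** The multiplier on the hazard ratio is [o/(o+u)] for rivaroxaban (h = 0.74 × 0.038) divided by the same for aspirin:

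| Rivaroxaban v aspirin | Multiplier |
|---|---|
| 0.5% v 0.25% | 0.997 |
| 1% v 0.5% | 0.995 |
| 2% v 1% | 0.989 |
| 1% v 2% | 1.011 |

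For scale, the standard error of log HR with 450 events is 2/√450 = 0.094. The 2% v 1% case shifts log HR by |ln 0.9894| = 0.011, about 11% of one standard error.

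**Shorter follow-up after the early stop** (assumed windows of 0–2 and 0.5–2.5 years, mean observed time 0.95 and 1.40 years). At 1% per year: 33 and 49 patients, 22 and 42 person-years per arm, shares 0.66% and 0.85%. At 2% v 1% the multiplier is 0.9934 and 0.9915.

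**Cross-check with a simpler model.** Take 3500 per arm, 1.93 patient-years each, 2% of patients in both arms survival-only with 1 year unobserved. Events not seen: 70 × (0.038 + 0.0281) = 4.6 of about 446, or 1.0%. Aspirin rate: 3.80 × (1 − 0.02/1.93) = 3.76. A 2-point difference between arms moves HR 0.740 to 0.732.

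**Bleeding, illustration only.** The documents give no bleeding rates for this trial's arms, so I use the 2.22 and 1.49 per 100 patient-years quoted in Protocol 1.3 from an earlier warfarin–aspirin trial. The true excess is 73.0 per 10,000 patient-years. Under the rule it is 72.8, 72.6 and 72.2 at 0.25%, 0.5% and 1% in both arms, 69.9 at 2% v 1%, and 73.8 at 1% v 2%.

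**The case against.** The strongest reply is that this hardly matters. The SAP calls the case rare and expects very few incomplete follow-ups. The safeguards are real: Protocol 5.2 asks for outcome events as well as vital status after treatment stops, through clinic, telephone, general practitioner or relative; Protocol 7.1.2.4 collects both at close-out; Protocol 7.3.1 screens adverse-event terms for missed events. Public-information checks follow only withdrawal of consent. The 2% rows assume twice the plan's whole loss rate, and the bleeding rates come from another trial. All of this stands. It bears on size, and it does not make the rule right for outcomes that were not ascertained.

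Two objections concern the remedy. An informant contact may yield survival status only, so a fallback to such contacts can still credit unobserved time. That is a limit, though a minor one, because the protocol uses informants for outcome follow-up. Also, counting late deaths while censoring survivors earlier creates a small upward bias. At 1% per year it is at most 2.1/244.8 = 0.86%, where 244.8 = 0.038 × 1.841 × 3500 is the expected number of primary events in the aspirin arm. The bound assumes that every late death counts.

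Finally, SAP Amendment 2 postdates the stop and reports the bleeding excess, so a change to the primary rule at that point needs care. This is a reason to show both rules side by side. A survival-only count might also appear in the separate table specifications, which are not among the documents; the SAP itself does not ask for one.

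**Conclusion.** The concern holds. SAP 4.5.3 states a primary-analysis rule that is correct for mortality and wrong for non-fatal stroke, systemic embolism, MI and bleeding.

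The effect is small. At an assumed 0.25% to 1% per year with equal arms, absolute rates are understated by about 0.3% to 1.1% and the hazard ratio does not move. An assumed two-to-one imbalance shifts the hazard ratio by about 0.3% to 1.1%. These figures rest on constant hazards and on assumed survival-only rates; the true number is not in the documents, and nothing in them indicates an imbalance. No trial conclusion is shown to change, including the early stop. The reason to correct the rule is that it is wrong as written and cheap to put right.

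**What to change.** - **SAP 4.5.1:** define a date of last outcome assessment, meaning the last contact at which stroke, systemic embolism, MI and bleeding were ascertained. Where the record does not show this, use the last visit or telephone contact with the patient or an informant, never a registry or public-information check.
- **SAP 4.5.3:** for these outcomes and composites containing them, censor patients without a documented event at the earlier of that date and the efficacy cut-off. Keep the survival-status date for all-cause mortality and for CV death alone.
- **Fatal components** (fatal stroke, fatal bleeding, the first secondary composite, the third net-benefit composite): state that adjudicated fatal events documented up to the cut-off count.
- **Sensitivity analyses:** one that censors at the last outcome assessment regardless of later deaths, and one that keeps the present rule. The first matters most for the first secondary composite, where deaths of unknown cause count as CV death.
- **Disposition:** report survival-only patients by arm as having incomplete outcome follow-up.

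The cost is wording in two sections, one derived date, one count by arm and two sensitivity runs. The documents do not show whether the CRF records that outcomes were asked about, hence the fallback. At 0.25% to 1% per year, 0.3% to 1.1% of person-years leaves the denominators. The change does not remove bias from informative withdrawal.

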#### **Censoring rules for on-treatment analyses**

For on-treatment analyses, all randomized subjects with at least one dose of study medication and without documentation of an event within the on-treatment data scope will be censored at the date of last double-blind dose of antithrombotic study treatment + 2 days or the date of the last trail contact, whatever comes first.

Note that if a subject stops treatment at the EOT visit and experiences an event up to 2 days thereafter, the event will be counted in this analysis but not in the primary analysis.

#### **4.5.4 Determination of baseline values**

Baseline is defined as the last non missing value until and including the day of randomization visit.

#### **4.5.5 Handling of repeated measurements - amended**

In case of multiple measurements per post baseline visits, the 1st non-missing value per visit will be taken for analysis.

In case of multiple assessments at different (unscheduled) post baseline visits for TEE, TTE, or questionnaires, the 1st non-missing assessment will be taken for analysis, others will be listed.

#### **4.6 Determination of sample size**

The study is event-driven and it is estimated that 7000 patients (3500 per treatment group) need to be randomized in order to have approximately 450 patients experiencing a confirmed primary efficacy outcome event using the ITT data scope. This number of events will allow the demonstration of superiority of rivaroxaban compared to ASA with regard to the primary outcome with a power of 90% and a one-sided level of significance  $\alpha=0.025$  under the following assumptions:

- An average yearly event rate of the composite primary efficacy outcome of 3.8% in the ASA group (4.0% for patients with age  $\geq 60$  years, 2.0% for 10% of patients with age  $< 60$  years)
- Effect size: A 30% RRR for stroke and systemic embolism in the rivaroxaban group compared to ASA
- Length of the recruitment period is 2 years and the total study duration is 3 years

- Approximately 10% of patients will permanently discontinue study medication in the first year and 7% in following years
- Approximately 5% of patients with a diagnosis of AF will switch to standard treatment during study conduct
- Approximately 3% patient deaths per year and 1% of patients lost to follow-up per year

Under these assumptions the expected RRR to be observed in this study would be 26% for the primary efficacy outcome.

The number of patients enrolled may be adjusted and the study duration may be adapted based on a blinded review of the observed overall event rate of confirmed primary efficacy outcomes during the study.

Sample size estimation was based on a Statistical Analysis Software (SAS) macro provided by [Shih](#).

## **5. Analysis Sets**

### **5.1 Assignment of analysis sets**

All subjects who have been randomized in the ESUS study are valid for assignment to analysis sets.

#### **5.1.1 Intention-to-treat analysis set (ITT)**

The intention-to-treat analysis set, also termed full analysis set in the International Conference on Harmonization (ICH) E9 guideline, will include all randomized subjects.

#### **5.1.2 Safety analysis set (SAF)**

The safety analysis set will include all randomized subjects who received at least one dose of study medication.

## **6. Statistical Methodology**

### **6.1 Population characteristics**

#### **6.1.1 Disposition**

The following will be tabulated overall and/or by treatment group:

- Study sample sizes (subjects enrolled, randomized, and valid for Safety analysis set) by region and country

- Study sample sizes by country and site
- Subject disposition
- Number of subjects and primary reasons for screening failures (only overall)
- Number of subjects and primary reasons for permanent discontinuation of study medication (by treatment group and overall for SAF)
- Number of subjects and primary reasons for discontinuation of study follow-up (by treatment group and overall for ITT and SAF)
- Number of subjects withdrew consent as well as Lost to Follow-up

Kaplan-Meier plots will be used to show:

- Time from randomization to last study medication,
- Time from randomization to last contact prior or equal to efficacy cut-off,
- Time from randomization to last trial contact

by treatment group and overall for ITT and SAF.

### 6.1.2 Demographics

Demographic variables and baseline characteristics will be summarized by treatment group and overall in the ITT and SAF. Summary statistics will be presented for metric variables. Frequency tables will be presented for categorical variables.

Demography includes age, gender, race, ethnicity, region, body height, body weight, body mass index (BMI) and smoking history. Age, body weight and BMI will each be given as continuous variable and categorized with the following categories:

- Age: <60; 60-75; >75 years (for publication: <75; ≥75 years)  
additionally <60; ≥60 years
- BMI: < 25; ≥ 25 to < 30; ≥ 30kg/m^2 (for publication: < 30; ≥ 30kg/m^2)
- Weight: <70; 70-90; >90 kg (for publication: <50; 50-100; >100 kg)

The following additional baseline characteristics will be analyzed:

- Sex: male; female
- Race: White; Black; Asian; American Indian or Alaska Native; Native Hawaiian or Other Pacific Islander; Not reported; Mixed
- Region: North America; South America; Western Europe; Eastern Europe; Asia (see Appendix B for definition)
- eGFR: <50; 50-80; >80 mL/min/1.73m^2

- Stroke or TIA prior to qualifying event: yes or no
- Time from qualifying stroke to randomization:  $\leq 30$  days; 30 days to 3 months;  $> 3$  months
- Presence of patent foramen ovale: present or absent / not known
- Cardiac rhythm monitoring:  $< 48$ ;  $\geq 48$  hours
- Hypertension: yes or no
- Diabetes: yes or no
- Heart failure: yes or no
- Tobacco use: never, former, current

